5.4 Planned Trial Calendar

The following dates are approximate. The actual dates may differ as, for example, the trial will not start until all the appropriate regulatory and ethical approvals have been obtained.

February 2014: IRB Submission

Planned trial period - FVFS (first visit, first subject) to LCLS (last contact, last subject): October 2014, February 2016

October 2014: First subject, first vaccination

January 2015: Last subject, last vaccination

February 2016: Last contact, last subject/Final study visit

July 2016: Assays Complete

January 2017: Final clinical study report submission

6 Enrollment and Retention of Trial Population

6.1 Recruitment Procedures

Subjects will be recruited for participation in this clinical trial. The site will ensure that any advertisements used to recruit subjects (letters, pamphlets, posters, etc.) are submitted to the IRB for approval.

6.2 Informed Consent Procedures

Informed consent is the process by which a subject voluntarily confirms his or her willingness to participate in a particular trial. Informed consent must be obtained before any study procedures are performed. The process is documented by means of a written, signed, and dated ICF. In accordance with GCP, prior to signing and dating the consent form, the subject must be informed by appropriate study personnel about all aspects of the trial that are relevant to make the decision to participate, and must have sufficient time and opportunity to ask any questions.

Any change to the content of the ICF must be approved by the IRB prior to the form being used.

If new information becomes available that may be relevant to the subject's willingness to continue participation in the trial, this will be communicated to him/her in a timely manner. Such information will be provided via a revised ICF or an addendum to the original ICF.

Informed consent forms will be photocopied. The original will be kept by the Investigator, and the copy will be kept by the subject.

Documentation of the consent process should be recorded in the source documents.

6.3 Screening Criteria

There are no screening criteria other than the inclusion and exclusion criteria.

6.4 Inclusion Criteria

Subjects must fulfill *all* of the following criteria in order to be eligible for trial enrollment:

- 1) Aged ≥ 18 to ≤ 60 years on the day of inclusion
- 2) Informed consent form has been signed and dated
- 3) Able to attend all scheduled visits and to comply with all trial procedures
- 4) Subject in good health, based on medical history and physical examination

^a “18 to 60 years” means from the day of the 18th birthday to the day before the 60th birthday

6.5 Exclusion Criteria

Subjects fulfilling *any* of the following criteria are to be excluded from trial enrollment:

1. Subject is pregnant, or lactating, or of childbearing potential (to be considered of non-childbearing potential, a female must be post-menopausal for at least 1 year, surgically sterile, or using an effective method of contraception or abstinence from at least 4 weeks prior to the first vaccination and until at least 4 weeks after the last vaccination)
2. Participation in the 4 weeks preceding the first trial vaccination, or planned participation during the present trial period, in another clinical trial investigating a vaccine, drug, medical device, or medical procedure.
3. Previous history of receiving the rabies vaccine
4. Previous history of receiving rabies immune globulin
5. Any major psychiatric disorder, such as severe depression, severe anxiety disorder, psychosis, schizophrenia, other major psychiatric disorders, or seizures. History of mild depression or anxiety disorder that is well controlled is not an exclusion criteria.
6. Any history of cardiac arrhythmias, such as: bradycardia, tachycardia, heart block, SVT, PAC, VT, VF, or any other conduction abnormalities.
7. Use of any immunosuppressive drug, including topical steroids of potency groups I, II or III within 30 days of the study period.
8. Any immunosuppressive disorder, such as HIV infection, common variable immunodeficiency, active cancers or chemotherapy.
9. History of renal insufficiency or requiring dialysis.
10. Have any condition that would, in the opinion of the site investigator, place the subject at an unacceptable risk of injury or render the subject unable to meet the requirements of the protocol.

11. Identified as an employee of the Investigator or study center, with direct involvement in the proposed study or other studies under the direction of that Investigator or study center, as well as family members (i.e., immediate, husband, wife and their children, adopted or natural) of the employee or the Investigator.
12. Temporary Exclusion Criteria: Moderate or severe acute illness/infection (according to investigator judgment) on the day of vaccination or febrile illness (temperature $\geq 38.0^{\circ}\text{C}$ [$\geq 100.4^{\circ}\text{F}$]). A prospective subject should not be included in the study until the condition has resolved or the febrile event has subsided. If the delay for the febrile illness exceeds the window between screening and vaccination, or if deemed necessary by the investigator, a prospective subject may be re-screened once the fever has resolved.

6.6 Medical History

Prior to enrollment, subjects will be assessed for pre-existing conditions and illnesses, both past and ongoing. This assessment will include a physical examination that will include, but not be limited to, the following body systems: neurological, heart, head, respiratory, and abdomen. Any pre-existing conditions and illnesses will be documented in the source document. Medical records will not be reviewed. Significant medical history (reported as diagnosis) including conditions for which the subject is or has been followed by a physician or conditions that could resume during the course of the study or lead to an SAE or to a repetitive outpatient care will be collected in the electronic case report form (eCRF).

Dates, medications, and body systems will be recorded; the information collected will not be coded.

For each condition, the data collected will be limited to:

- Diagnosis with dates (this is preferable to reporting signs and symptoms)
- Presence or absence of the condition at enrollment

Vitals signs will include temperature, blood pressure, and pulse taken while the subject is in a resting position.

At subsequent visits, a history-driven physical examination will include, but not be limited to, the following body systems: neurological, heart, head, respiratory, and abdomen. The necessity of this physical examination is determined through conversation between the study staff and the subject about the subject's current medical status.

6.7 Contraindications for Subsequent Vaccinations

6.7.1 Temporary Contraindications

Should a subject experience one of the conditions listed below, the Investigator will postpone further vaccination until the condition is resolved.

- Ongoing clinical AE or biological abnormality related to the trial vaccination
- Febrile illness (temperature $\geq 38.0^{\circ}\text{C}$ [$\geq 100.4^{\circ}\text{F}$]) or moderate or severe acute illness/infection on the day of vaccination, according to Investigator judgment.

Postponement must still be within the timeframe for vaccination indicated in the Tables of Study Procedures. If the delay for the febrile illness exceeds the window between screening

and vaccination, or if deemed necessary by the investigator, a prospective subject may be re-screened once the fever has resolved.

- Acute illness on day of vaccination that the investigator determines the subject to be ineligible for vaccine that day.

6.7.2 Definitive Contraindications

Should a subject experience one of the conditions listed below, the Investigator will discontinue vaccination:

- Pregnancy, as indicated by a positive urine test on vaccination days.
- An anaphylactic or other significant allergic reaction to the previous dose of vaccine
- Known or suspected congenital or acquired immunodeficiency; or receipt of immunosuppressive therapy such as anti-cancer chemotherapy or radiation therapy within the preceding 6 months; or long-term systemic corticosteroid therapy (prednisone or equivalent for more than 2 consecutive weeks within the past 3 months)
- SAE related to the study vaccine following the trial vaccination
- Participation in another clinical trial investigating a vaccine, drug, medical device, or medical procedure
- Deprived of freedom by an administrative or court order, or in an emergency setting, or hospitalized involuntarily. Subjects will not be withdrawn due to contraindication but will be followed up for safety and possibly immunogenicity assessment.

Note: If a subject who has already received at least 1 dose of the study vaccine, experiences a contraindication to further vaccination during the trial, they will continue to be followed for immunogenicity assessments and will not be discontinued from the trial; however, no additional vaccinations will be administered.

6.8 Other Conditions-for-Withdrawal beyond Definitive Contraindications

Subjects will be informed that they have the right to withdraw from the trial at any time.

A subject may be withdrawn from the study:

- At the discretion of the Investigator or Sponsor due to safety concerns without the subject's permission (withdrawal)
- At the request of the subject (dropout)

The following will result in automatic withdrawal or exclusion of a subject from the study:

- Significant noncompliance with the protocol, based on the Investigator's judgment

The reason for a withdrawal or dropout should be clearly documented in the source documents and on the eCRF.

Withdrawn subjects will not be replaced.

6.9 Lost to Follow-up Procedures

In the case of subjects who fail to return for a follow-up examination, documented reasonable effort (i.e., documented telephone calls) should be undertaken to locate or recall them, or at least to determine their health status while fully respecting their rights. These efforts should be documented in the source documents.

6.10 Classification of Subjects Who Discontinue the Trial

For any subject who discontinues the trial prior to completion, the most serious reason for early termination will be checked in the eCRF. Reasons will be listed from the most serious to the least serious as follows:

- **Serious adverse event:** To be used when a subject drops out of or is withdrawn from the study by the Investigator because of the occurrence of an SAE, as defined in Section 18.
- **Other adverse event:** To be used when a subject drops out of or is withdrawn from the study by the Investigator because of the occurrence of an AE other than an SAE, as defined in Section 17.
- **Non-compliance with protocol:** To be used when the Investigator withdraws a subject from the study because of failure to follow protocol guidelines (e.g., not attending visits, not being available for telephone calls, not providing blood samples). This termination category may also be used if it is retrospectively discovered that a subject did not fulfill the eligibility criteria. The Investigator will provide a comment as to the specific cause of non-compliance.
- **Lost to follow-up:** To be used when the Investigator withdraws a subject from the study because of failure to establish contact, as outlined in Section 6.9. The Investigator will provide documentation that contact was attempted (i.e., return of unsigned certified letter receipt).
- **Voluntary withdrawal not due to an adverse event:** To be used when a subject drops out of the study for any reason other than those listed above.

6.10.1 Follow-up of Discontinuations

The site should complete all scheduled follow-ups with any subject who has prematurely terminated the trial because of an SAE, other type of AE, non-compliance with the protocol, or loss of eligibility, including definitive contraindications. Discontinued subjects will be followed up to 6 months after the last vaccination.

For subjects where the reason for early termination was lost to follow-up or if the subject withdrew informed consent and specified that they do not want to be contacted again and it is documented in the source document, the site will not attempt to obtain further information.

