20.3 Per-Protocol Analysis Set

The Per-Protocol (PP) analysis set will include all subjects who had no protocol deviations at the time that the data was collected. Three PP analysis sets will be produced for the primary objective that will contain separate data from blood drawn on day 0, day 28 and day 372, respectively. Descriptive analysis of the secondary endpoint will require a fourth per protocol analysis set for blood drawn on day 365. Subjects will be excluded from the PPAS for the following reasons:

- 1) Subject did not meet all protocol-specified inclusion/exclusion criteria or definitive contraindications (only for the second and third vaccination).
- 2) Subject did not receive the correct number of injections.
- 3) Administration of vaccine was not done as per protocol (site and route of administration).
- 4) Subject did not receive vaccine in the proper time window defined in the tables of the study procedures.
- 5) Subject did not provide a post-dose serology sample in the proper time window defined in the tables of the study procedures.

Subjects will remain in this population as long as they do not meet one of the above criteria, except for blood sampling timing and validity of the serology test result*. A PP set will be defined for each injection.

*Note: For example, a subject whose time period is outside the defined visit window only between the first injection and the blood sample taken after the first injection will be excluded from PP1 but may be kept in PP2 or PP3.

Subjects will be analyzed by the vaccine group to which they were randomized, subject to the exclusion criteria above

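### Section 6.10.1 stops all contact with subjects recorded as lost to follow-up, and sets a six-month limit for other discontinued subjects that ends before the Day 365 and 372 draws

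*Protocol*

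**What the plan says.** Protocol 6.10.1 sorts discontinued subjects into two classes.

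- **Lost to follow-up, or consent withdrawn with a documented wish not to be contacted:** "the site will not attempt to obtain further information".
- **Stopped for an SAE, another AE, non-compliance or loss of eligibility:** the site is to complete every scheduled follow-up. The next sentence limits follow-up of discontinued subjects to six months from the last vaccination.

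Three neighbouring sections bear on this.

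- **Section 6.8** lists significant non-compliance under "The following will result in automatic withdrawal or exclusion of a subject from the study".
- **Section 6.9** asks for "documented reasonable effort (i.e., documented telephone calls") when a subject fails to return. It sets no minimum number of attempts and no period.
- **Section 6.10** gives as examples of non-compliance "not attending visits, not being available for telephone calls, not providing blood samples". It assigns lost to follow-up when the Investigator withdraws a subject "because of failure to establish contact, as outlined in Section 6.9", with "return of unsigned certified letter receipt" as evidence. Where several reasons apply, "the most serious reason for early termination will be checked in the eCRF", and non-compliance is listed above lost to follow-up.

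On the analysis side, the note in 20.3, repeated in the SAP, says that a subject whose first post-injection sample is mistimed "will be excluded from PP1 but may be kept in PP2 or PP3".

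**The concern.** Failing to reach a subject is not a refusal by that subject. Section 6.10.1 nevertheless gives both the same permanent consequence, and nothing reopens contact before the one-year visits. The interval from Day 77 to Day 365 is the longest in the schedule, so a subject who moved or was busy in the first months may well be reachable again by then.

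The rule also fits poorly with the rest of the plan. Sections 6.7.2 and 6.10.2 keep contraindicated and pregnant subjects in the trial for immunogenicity without further doses. The per-protocol note allows an early sampling problem to leave later sets intact.

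At stake are the Day 365 and Day 372 percentages, which the synopsis and sections 20.1 and 20.2 make the secondary and primary one-year results. Section 6.8 rules out replacement, and section 21.1 and the SAP rule out imputation, so every lost subject reduces the denominator.

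**Working it through.** **Plan's own figure.** Four vaccine arms of 12 and two control arms of 6 give 4 × 12 + 2 × 6 = 60, as in section 22. The number was chosen empirically and no dropout rate is given, so there is no power figure to recompute.

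**Timing of the six-month limit.** Inputs: last priming dose on Day 7 (Groups 3 and 4) or Day 21 (Groups 1 and 2); visit windows of ±15 days at Days 365 and 372 (tables of study procedures). Assumption: six months is 180 to 184 days.

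- Last dose Day 7: 7 + 180 = 187 to 7 + 184 = 191.
- Last dose Day 21: 21 + 180 = 201 to 21 + 184 = 205.
- Earliest in-window draws: 365 − 15 = Day 350 and 372 − 15 = Day 357.
- Shortfall before the Day 365 window: 350 − 205 = 145 days to 350 − 187 = 163 days.

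Read literally, a discontinued subject who has not been boosted leaves follow-up before either draw, even when the recorded reason is one for which all follow-ups are to be completed. The interval with no scheduled contact is 365 − 77 = 288 days.

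**Who is affected.** A subject unreachable at Day 7, or at Day 21 in a three-dose arm, misses a dose and fails per-protocol reasons 2 and 4 in section 20.3. The point therefore concerns subjects who completed priming and were then unreachable around Day 28 or 77. Such a subject could still give a per-protocol Day 365 pre-boost sample. A per-protocol Day 372 sample would also require the boost to have been given under the existing rules.

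**Size.** One subject in an arm of 12 is 1/12 = 8.3 percentage points. The documents state no loss rate, so the range shown is an assumption: 0 to 3 lost of 12. The exact (Clopper-Pearson) 95% lower limit when all n observed subjects respond is 0.025^(1/n).

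| Lost of 12 | Observed, all protected | Exact 95% lower limit | Lost counted as unprotected |
|---|---|---|---|
| 0 | 12/12 | 73.5% | 100% |
| 1 | 11/11 | 71.5% | 91.7% |
| 2 | 10/10 | 69.2% | 83.3% |
| 3 | 9/9 | 66.4% | 75.0% |

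If 10 of 12 are truly protected (83.3%, exact 95% CI 51.6 to 97.9%) and two are lost, the reported result is:

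- 8/10 = 80% (CI 44.4 to 97.5%) if both lost subjects were protected;
- 10/10 = 100% (CI 69.2 to 100%) if neither was.

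**Share due to this rule.** Only subjects whom renewed contact would bring back count. If two are lost and all observed subjects respond, recovering neither, one or both (assuming those recovered respond) gives lower limits of 69.2%, 71.5% or 73.5%. That is a gain of 0, 2.3 or 4.3 points.

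**The case against.** **The category overlap might look like the cause.** The descriptions of non-compliance and lost to follow-up do overlap, and their follow-up duties are opposite. A reader might infer that a site can pick the label that ends contact, or that a subject missed once early on need not be contacted again. The documents do not support this. Section 6.10 records the most serious reason and ranks non-compliance higher, so a subject who fits both goes to the class whose follow-ups are to be completed. Section 6.9 requires documented effort after any missed follow-up examination before the lost label can apply. The overlap is a wording point.

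**Day 77 might look unused.** The SAP specifies no Day 77 table. But section 20.1 calls for descriptive statistics at each blood draw, and a kinetic analysis on the full analysis set is planned, so Day 77 cannot be called irrelevant.

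**The per-protocol note is narrow.** It concerns a mistimed sample, not an absent one, and does not address contact. It shows that later samples could be accepted, not that the analysis depends on re-contact.

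**The evidence rules may be compatible.** Telephone calls and a certified letter can be read as successive steps, since 6.10 refers back to 6.9.

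**The study is descriptive.** No formal hypothesis is tested, Day 28 is also a primary timepoint, and the interval effect is modest.

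These objections narrow the point. They leave in place the permanent no-contact rule for subjects who never refused contact, and the six-month limit that ends before Day 350.

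**Conclusion.** The concern holds in a limited form. Section 6.10.1 ends contact for anyone recorded as lost to follow-up, with no exception for the one-year endpoint draws. For other discontinued subjects it gives two statements that cannot both be followed, because the six-month limit ends 145 to 163 days before the Day 365 window opens (last dose Day 7 or 21, six months taken as 180 to 184 days).

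Each avoidable loss is worth 8.3 percentage points in an arm of 12. The total effect cannot be stated, because it depends on an unstated loss rate and on how many subjects renewed contact would recover.

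A reader might also infer bias between arms, since the trial is open-label and site staff record the reason for discontinuation. Differential loss is possible, but nothing in the documents links the recorded reason to arm or titer, so it is not shown. The case for change is that endpoint data can be recovered cheaply; no planned analysis is invalidated.

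**What to change.** 1. In 6.10.1, limit the no-further-contact rule to subjects who withdrew consent and asked not to be contacted.
2. Require a documented re-contact attempt before the Day 365 window opens for every vaccine-arm subject who has not refused contact.
3. Reconcile the six-month sentence with the duty to complete scheduled follow-ups, so that it does not end blood sampling before Days 365 and 372.
4. Make 6.8, 6.9 and 6.10 consistent with this. State whether missed visits or failed contact alone trigger automatic withdrawal, separate the two category definitions, and give one standard of contact evidence with a minimum number of attempts.

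Whether further vaccine is given stays under the existing rules and is not part of this change.

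The cost is protocol wording and a little coordinator time for calls or letters.

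The SAP is dated December 2016 and section 5.4 planned last contact for February 2016. If follow-up has already ended, the useful step is in reporting: show the reason and day of discontinuation by group next to the Day 365 and Day 372 denominators. The SAP's disposition section currently plans only counts of doses received.

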6.10.2 Follow-up and Reporting of Pregnancies

Pregnancy is an exclusion criterion for enrollment in this study, but a subject could potentially become pregnant during her participation. In case of pregnancy and if at least one dose of the study vaccines has been administered, the subject will not be discontinued from the trial and will

be followed for immunogenicity assessment. However, no additional vaccination will be administered.

All pregnancy cases should be reported if they occurred during the study. Study staff must then maintain contact with the subject to obtain information about the outcome—i.e., details about the delivery and the newborn, or about pregnancy termination.

Pregnancy itself is not considered an AE, but any complications during pregnancy are to be considered as AEs, and in some cases could be considered SAEs. Spontaneous abortions, fetal death, stillbirth, and congenital anomalies reported in the baby are always considered as SAEs, and the information should be provided using an SAE form.

7 Safety Emergency Coverage

Subjects in the trial will be given contact numbers for the PI and study team members in the event of an emergency related to the trial. A study investigator will be available at all times for study related emergencies. If emergency health care is needed, subjects should seek care through the 911 system or local emergency services. Study team contact numbers should be used to notify the study team of an emergency after emergent health care issues have been handled.

8 Modification of the Trial and Protocol

Any amendments to this trial plan and protocol must be discussed with WRAIR. If agreement is reached concerning the need for an amendment, the PI will be responsible for completing the amendment and creating a new version of the protocol will replace the earlier version. All substantial amendments e.g. that affect the conduct of the trial or the safety of subjects, require IRB approval, and must also be forwarded to regulatory authorities.

An administrative amendment to a protocol is one that modifies some administrative or logistical aspect of the trial but does not affect its design or objectives or have an impact on the subjects' safety. Regulatory authorities need only be notified about administrative changes. Sites will be required to submit any administrative amendments to their IRB for notification and/or approval. The Investigator is responsible for ensuring that changes to an approved trial, during the period for which IRB approval has already been given, are not initiated without IRB review and approval, except to eliminate apparent immediate hazards to subjects.

9 Vaccines Administered

Subjects in Group 1 will receive 3 doses of Rabies vaccine administered IM at Days 0, 7,21 and 365.

Subjects in Group 2 will receive 3 doses of Rabies vaccine administered ID at Days 0, 7,21 and IM at Day 365.

Subjects in Group 3 will receive 2 doses of Rabies vaccine administered IM at Days 0,7 and 365.

Subjects in Group 4 will receive 2 doses of Rabies vaccine administered ID at Days 0,7, and IM at Day 365.

Subjects in Group 5 will receive 1 dose of Human Serum Albumin administered IM at Day 0.

Subjects in Group 6 will receive 1 dose of Human Serum Albumin administered ID at Day 0.

